6.2.2 Primary Analysis

The primary analysis for this study will be a descriptive comparison of glycemic response during exercise and early recovery between the mini-dose glucagon group (strategy 3) and the control group. Summary statistics will be calculated. In the event that exercise is terminated early due to glucose <70 mg/dL and the participant is treated for hypoglycemia, the nadir glucose value will be carried forward through early recovery.

To obtain a test of significance, a treatment comparison of glucose during exercise and early recovery will be completed using a linear mixed model with repeated measures that accounts for the correlation due to the cross-over design and the correlation due to multiple measures, adjusting for baseline glucose level and period. Regression diagnostics will be performed and if the distribution of residuals is skewed, non-parametric methods and transformations will be considered.

6.2.3 Secondary Outcomes

The following outcome measures will also be analyzed.

- Occurrence of hypoglycemia (<70 mg/dL) as measured by YSI analysis during exercise or early recovery

- 661 • Occurrence of hyperglycemia (≥ 270 mg/dL) as measured by YSI analysis in the following
- 662 time periods: during exercise, after exercise in early recovery/prior to meal ingestion and for
- 663 90 minutes after the meal (2 hours after the end of exercise)
- 664 • Glucose levels during exercise and early recovery (venous plasma)
- 665 • Glucose levels after a standardized meal (glucose area under the curve analysis, venous
- 666 plasma)
- 667 • Glucose levels in late recovery (afternoon and overnight following the exercise protocols-
- 668 CGM analysis)
 - 669 ○ Mean
 - 670 ○ Nadir
 - 671 ○ Area above and below curve threshold (i.e. area above or below 70-180 mg/dL)
 - 672 ○ % of time in range (70-180 mg/dL)
 - 673 ○ % of time below 70 mg/dL
 - 674 ○ Occurrence of hypoglycemia (< 70 mg/dL) overnight
- 675 • Carbohydrate intake (before, during and for 30 min post exercise)
- 676 • HR and ratings of perceived exertion
- 677 • Insulin and glucose counterregulatory hormones (glucagon, GH, catecholamines, cortisol)
- 678 • Inflammatory cytokines (TNF α , IL-6)
- 679 • Metabolites (nonesterified fatty acids, β -hydroxybuterate, lactate)

680
681

6.2.4 Secondary Analyses

683 The primary and secondary outcomes will largely be examined in a descriptive manner. Summary
684 statistics will be calculated by treatment strategy. For binary variables, percentage of participants
685 developing the outcome, with 95% confidence interval, will be calculated by strategy. Each of the
686 three strategies will be compared to the control in secondary analyses.

687 Tests of significance will also be obtained using a 2-sided alpha of 0.05. For binary variables, a
688 generalized linear mixed model with a logistic link function for a binary outcome will be fit to
689 assess differences between strategy 3 and each of the other strategies. The model will be adjusted
690 for baseline glucose and period. For continuous variables, repeated measures linear regression
691 models will be fit adjusting for period and where applicable the baseline value. Regression
692 diagnostics will be performed and if the distribution of residuals is skewed, non-parametric methods
693 and transformations will be considered. No formal correction will be made for multiple
694 comparisons.

696

6.3 Safety Analyses

697 Adverse events will be tabulated by strategy:

698

- 699 • Proportion reporting at least one adverse event
- 700 • Proportion with an adverse event thought by investigator to be related to strategy
- 701 • Proportion who stopped study treatment in response to an adverse event
- 702 • Total number of adverse events reported
- 703 • Number of serious adverse events reported
- 704 • Number of non-serious adverse events reported

705

706 Adverse events will be tabulated by MedDRA categories with frequencies compared between
707 strategies. Similar models and diagnostics will be performed as described for the efficacy outcomes
708 above.
709
710

711 **CHAPTER 7: DATA COLLECTION AND MONITORING**
712

713 **7.1 Data Collection**

714 Data will be collected directly on electronic case report forms and will be considered source
715 documents when data are directly entered. Other data will be collected from participant logs,
716 downloads of devices and from laboratories processing the samples.
717

718 **7.2 Quality Assurance and Monitoring**

719 Designated personnel from the Coordinating Center will be responsible for maintaining quality
720 assurance (QA) and quality control (QC) systems to ensure that the trial is conducted and data
721 are generated, documented and reported in compliance with the protocol, GCP and the applicable
722 regulatory requirements.
723

724 A risk-based monitoring (RBM) plan will be developed and revised as needed during the course
725 of the study. The RBM plan will focus mainly on data related to eligibility, adverse events and
726 the primary efficacy analysis. As much as possible, remote monitoring will be performed in
727 real-time, with on-site monitoring performed to evaluate the verity and completeness of the key
728 site data.
729

730 Xeris, the Jaeb Center for Health Research, or their representatives may visit the study facilities
731 at any time in order to maintain current and personal knowledge of the study through review of
732 the records, comparison with source documents, observation and discussion of the conduct and
733 progress of the study.
734
735

736

CHAPTER 8: REFERENCES

737

738 1) Chu L, Hamilton J, Riddell MC (2011) Clinical management of the physically active patient
739 with type 1 diabetes. *Physiol Sports Med* 39: 64–77.

740

741 2) West DJ, Morton RD, Bain SC, Stephens JW, Bracken RM (2010) Blood glucose responses

T1D Exchange[®]

1

2

THE USE OF MINI-DOSE GLUCAGON TO PREVENT EXERCISE-INDUCED HYPOGLYCEMIA IN TYPE 1 DIABETES

Statistical Analysis Plan v. 1.0
Protocol v. 3.0

February 24, 2017

3

Version History

Version Number	Author	Approver	Effective Date	Study Stage	Revision Description
1.0	[name]	[name]	February 24, 2017	Data collection in progress; no analyses performed	Original version

4

5

6 **1.0 Study Overview**

7 This project focuses on the development of a new strategy for the prevention of exercise-
8 associated hypoglycemia using mini-dose glucagon.

9
10 The primary objective of the protocol is to determine if the administration of mini-dose glucagon
11 administered subcutaneously just before exercise produces better glucose stability than no
12 adjustments for moderate intensity exercise in patients with T1D. It will also be assessed
13 whether mini-dose glucagon before exercise produces better glucose stability than basal insulin
14 reductions or extra carbohydrate consumption.

15
16 Subjects 18 to <65 years old with type 1 diabetes (T1D) for at least 2 years and receiving daily
17 insulin who exercise regularly will be enrolled into the multi-center study. The study is a
18 randomized, 4-way crossover trial.

19
20 Each participant will undergo four aerobic exercise sessions (in random order) in the
21 CRC, with different strategies for glucose regulation:

- 22 • Control Trial: Fasted exercise, no basal insulin reduction
- 23 • Strategy 1: Fasted exercise, basal insulin reduction only (50% reduction in basal rate
24 five minutes before exercise, for the duration of the exercise)
- 25 • Strategy 2: Fasted exercise, no basal adjustment + pre-exercise glucose tabs (buccal
26 route-40 grams in total)
- 27 • Strategy 3: Fasted exercise, no basal adjustment + pre-exercise mini-dose glucagon
28 (sc)

29
30 In all 4 sessions, aerobic exercise will be performed in the fasted state (before a
31 standardized meal) for 45 minutes at ~50-55% of the participant’s pre-determined aerobic
32 capacity (determined by VO2 max test at screening visit).

33
34 **2.0 Sample Size**

35 A target of 16 subjects, with replacement of any participants who do not complete the study, was
36 selected as a reasonable sample size for this feasibility study. Considering the primary outcome
37 of glucose, power was approximated using a t-test. The table below provides power estimates
38 based on a paired t-test comparing glucose during the mini-dose glucagon treatment and glucose
39 during the control treatment.

40
41 **Power Estimates***

Mean difference (mg/dL)	Correlation						
	0.2	0.3	0.4	0.5	0.6	0.7	0.8
20	32%	35%	40%	47%	55%	68%	84%
25	46%	51%	57%	65%	74%	85%	96%
30	60%	66%	73%	80%	88%	95%	99%
35	74%	79%	85%	91%	96%	99%	>99%

42 *Power was calculated for a sample size of 16 participants with a two-sided alpha of 0.05 and assuming a standard
43 deviation of 40 mg/dL for each treatment. (A previous DirectNet exercise study was considered when estimating
44 standard deviation [Tsalikian 2006].

45

46 **3.0 Analysis Plan**

47

48 **3.1 Sample collection**

49 Blood samples collected through a venous catheter with plasma glucose measured by an YSI
50 analyzer. Blood samples will be collected at:

- 51 • Baseline (at -30, -15, -5, 0 min)
- 52 • During exercise (at 5, 10, 15, 25, 35, 45 min)
- 53 • In recovery post exercise (at 50, 55, 60, 75 min)
- 54 • Regularly following a standardized mixed meal for 90 minutes (at 90, 105, 120, 135, and
55 165 min)

56

57 **3.2 Definitions of Time Periods**

- 58 • Exercise—45 minutes of scheduled exercise, even if participant terminated exercise early
- 59 • Early recovery—all time points through 30 minutes post exercise session
- 60 • Late recovery—all CGM data through noon the day after each exercise session will be
61 included. Periods of interest during late recovery include the below. Timing of meals
62 indicated on participant log; if log is missing or incomplete, meal timing will be
63 estimated.
 - 64 ○ Standard meal during study (30 minutes post exercise) to standard box lunch
65 provided at discharge
 - 66 ○ Box lunch provided at discharge to dinner (of participant's choice)
 - 67 ○ Dinner to 10:00 PM
 - 68 ○ 10:00 PM to 8:00 AM the day following exercise
 - 69 ○ 8:00 AM to noon the day following exercise

70

71 **3.3 Primary Outcome**

72 The primary outcome for this study will be glucose, as measured by YSI analysis, during
73 exercise and early recovery.

74

75 **3.3.1 Primary Analysis**

76 The primary analysis for this study will be a descriptive comparison of glycemic response during
77 exercise and early recovery between the mini-dose glucagon group (strategy 3) and the control
78 group. Summary statistics will be calculated. In the event that exercise is terminated early due to
79 glucose <70 mg/dL and the participant is treated for hypoglycemia (or if participant is treated for
80 hypoglycemia during early recovery [prior to the meal]), the nadir glucose value will be carried
81 forward through the end of early recovery.

82

83 Analysis will follow the intent-to-treat principle with each visit allocated to one of the above
84 strategies (Section 1.0) according to the randomization assignment. Analysis will include
85 subjects who completed both the mini-dose glucagon and the control exercise session visits with
86 baseline glucose and at least three YSI glucose measurements during exercise and at least two
87 YSI glucose measurements during early recovery available from each visit.

88

89 To obtain a test of significance, a treatment comparison of glucose during exercise and early
90 recovery will be completed using a linear mixed model with repeated measures that accounts for
91 the correlation due to the cross-over design and the correlation due to multiple measures,
92 adjusting for baseline glucose level and any period effect. Regression diagnostics will be
93 performed and if the distribution of residuals is skewed, non-parametric methods and
94 transformations will be considered.

95

96 **3.4 Secondary Outcomes**

97 The following outcome measures will also be analyzed.

- 98 • Occurrence of hypoglycemia (<70 mg/dL) as measured by YSI analysis during exercise
99 or early recovery, at the visit level
- 100 • Occurrence of hyperglycemia (≥ 250 mg/dL) as measured by YSI analysis in the
101 following time periods: during exercise, after exercise in early recovery/prior to meal
102 ingestion and for 90 minutes after the meal (2 total hours after the end of exercise), at the
103 visit level
- 104 • Glucose levels after a standardized meal (glucose area under the curve analysis)
- 105 • Glucose levels in late recovery (afternoon and overnight following the exercise protocols-
106 CGM analysis)
 - 107 ○ Mean
 - 108 ○ Nadir
 - 109 ○ Area above and below curve threshold (i.e. area above or below 70-180 mg/dL)
 - 110 ○ % of time in range (70-180 mg/dL)
 - 111 ○ % of time below 70 mg/dL
 - 112 ○ Occurrence of hypoglycemia (<70 mg/dL) overnight

113

114 For sensor data after an exercise session to be included in the analysis, a subject must have at
115 least 12 hours (i.e., 144 CGM readings) from the window after the exercise session through noon
116 the following day.

117

118 **3.4.1 Secondary Analyses**

119 The secondary outcomes will largely be examined in a descriptive manner. Summary statistics
120 will be calculated by treatment strategy. For binary variables, percentage of participants
121 developing the outcome, with 95% confidence interval, will be calculated by strategy. Strategy 3
122 will be compared with each of the other strategies in secondary analyses.

123

124 Tests of significance will also be obtained using a 2-sided alpha of 0.05. For binary variables, a
125 generalized linear mixed model with a logistic link function for a binary outcome will be fit to
126 assess differences between strategy 3 and each of the other strategies. The model will be
127 adjusted for baseline glucose and any period effect. For continuous variables, a repeated
128 measures linear regression model will be fit adjusting for period and where applicable the
129 baseline value. One model will be run per outcome measure, with multiple pairwise comparisons
130 from the same model. Regression diagnostics will be performed and if the distribution of
131 residuals is skewed, non-parametric methods and transformations will be considered. No formal
132 correction will be made for multiple comparisons.

133

134

135 **3.5 Exploratory Analyses**

136 The following outcome measures may be explored:

- 137 • Carbohydrate intake (before, during and for 30 min post exercise)
- 138 • HR and ratings of perceived exertion
- 139 • Insulin and glucose counterregulatory hormones (glucagon, GH, catecholamines,
140 cortisol)
- 141 • Inflammatory cytokines (TNF α , IL-6)
- 142 • Metabolites (nonesterified fatty acids, β -hydroxybuterate, lactate)

143
144 **3.6 Additional Tabulations**

- 145 • Baseline characteristics
- 146 • Number of subjects who did not complete the study and reasons for discontinuation

147
148 **4.1 Safety**

149 Information from all subjects throughout the study will be used to assess safety.

150
151 **4.1.1 Adverse Event Definitions**

152 A reportable adverse event is any untoward medical occurrence in a study participant,
153 irrespective of whether or not the event is considered treatment-related, that occurs 12 hours
154 prior, during, or the day after each exercise session, except for hypoglycemia, hyperglycemia,
155 injection-related, and exercise-induced events which are only reported as adverse events when
156 the criteria described below are met.

157
158 Hypoglycemic events are recorded as Adverse Events if the event required IV dextrose or IM
159 glucagon to treat.

160
161 Hyperglycemic events are recorded as Adverse Events if evaluation or treatment was obtained
162 from a health care provider or if the event involved DKA, as defined by the Diabetes Control and
163 Complications Trial (DCCT) and described below, or in the absence of DKA if evaluation or
164 treatment was obtained from a health care provider or an acute event involving hyperglycemia or
165 ketosis.

166
167 Hyperglycemic events are classified as DKA if all of the following are present:

- 168 • Symptoms such as polyuria, polydipsia, nausea, or vomiting
- 169 • Serum ketones >1.5 mmol/L or large/moderate urine ketones
- 170 • Either arterial blood pH <7.30 or venous pH <7.24 or serum bicarbonate <15
- 171 • Treatment provided in a health care facility

172
173 Injection-related events are recorded as Adverse Events if sufficiently severe that treatment was
174 given.

175
176 Exercise-induced events are recorded as Adverse Events if the subject falls during the exercise
177 protocol or develops signs or symptoms of a myocardial infarction, poor perfusion (pallor,
178 cyanosis), angina, pathologic arrhythmia, or another medical condition not expected to occur
179 during or following the exercise.

180

181 **4.1.2 Safety Analysis**

182 Adverse events will be tabulated by strategy.

- 183
- 184 • Proportion reporting at least one adverse event
 - 185 • Proportion with an adverse event thought by investigator to be related to study treatment
 - 186 • Proportion who stopped study treatment in response to an adverse event
 - 187 • Total number of adverse events reported
 - 188 • Number of serious adverse events reported
 - 189 • Number of non-serious adverse events reported

190 Adverse events will be tabulated by MedDRA categories with frequencies compared between
191 strategies. Similar diagnostics and models will be performed as described for the efficacy
192 outcomes above.

193

194

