3.2.2 During Exercise Sessions

At each visit, participants will complete one of the following four exercise sessions (sequence of sessions determined by randomization):

339 Control Trial: No basal insulin adjustment, no carbohydrate intake until glucose drops <70
340 mg/dL. Then 20 grams of dextrose will be given orally.
341 Strategy 1: Basal insulin reduction to 50% five minutes before the start of exercise. Basal
342 insulin rate will be returned to usual rate 45 minutes after the start of exercise.
343 Strategy 2: Dextrose tabs taken orally (20 grams) five minutes before the start of exercise and
344 at 30 minutes of exercise (total 40 grams).
345 Strategy 3*: Glucagon (150 µg) five minutes before the start of exercise (SQ-abdomen).

346
347 *The dose for strategy 3 will likely be 150 µg, but may be modified to be lower or higher, with a
348 possible range of 75-300 µg. One or more pilot phases of up to 6 participants will be conducted
349 prior to study initiation to determine the most appropriate dose.

350
351 The participant's pump will be blinded during the control trial, strategy 1, and strategy 3 and an
352 injection of saline will be given during the control trial and strategy 1 so that participant is
353 blinded to strategy.

354
355 Exercise will consist of moderate intensity aerobic activity (treadmill jogging/brisk walking)
356 performed at 50-55% of predetermined VO₂max for 45 minutes. Continuous heart rate
357 measurements will be conducted along with intermittent ratings of perceived exertion (Borg 6-20
358 scale).

359
360 Exercise will be terminated if:
361 • Glucose is <70 mg/dL; participants will be treated for hypoglycemia (initially 20 grams
362 of oral dextrose tabs or IV dextrose or IM glucagon depending on the severity of the
363 hypoglycemia).
364 • Participants experience dizziness, pallor and other symptoms of poor perfusion and or
365 exercise intolerance

366
367 Any treatment given will be recorded.

368
369 Participants who are not able to complete an exercise session due to termination will still
370 complete remaining study procedures as outlined in sections 3.2.3 and 3.2.4.

371 372 **3.2.3 Following Exercise Sessions**

373 Following each exercise session, the participant will rest for 30 minutes and then consume a
374 standardized meal containing 44-50 grams of carbohydrate that constitute ~55% of calories,
375 together with ~20% calories from protein and ~25% calories from fat. The amount of bolus

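### Baseline glucose is undefined, and the plan's list of baseline samples includes 0 minutes, five minutes after all three active strategies start (minor, cheap to fix)

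*SAP*

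**What the plan says.** **Sampling.** SAP 3.1 and Protocol 3.2.4 give the same schedule. The first group is "Baseline (at -30, -15, -5, 0 min"; the exercise samples then run from 5 to 45 minutes. The session lasts 45 minutes, so 0 minutes is the start of exercise.

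**Start of the strategies.** Protocol 3.2.2 has, for strategy 1, "Basal insulin reduction to 50% five minutes before the start of exercise"; for strategy 2, "Dextrose tabs taken orally (20 grams) five minutes before the start of exercise", with a second dose at 30 minutes; and for strategy 3, glucagon "five minutes before the start of exercise (SQ-abdomen". The SAP repeats the five-minute timing only for strategy 1 (Section 1.0).

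**Use of baseline glucose.**
- Primary mixed model: "adjusting for baseline glucose level and period" (Protocol 6.2.2) and "adjusting for baseline glucose level and any period effect" (SAP 3.3.1).
- Binary secondary models: adjusted "for baseline glucose and period" (Protocol 6.2.4), and similarly in SAP 3.4.1. Continuous secondary outcomes take a baseline value where one applies.
- Primary analysis set: each of the two visits must supply "baseline glucose and at least three YSI glucose measurements during exercise and at least two" in early recovery (SAP 3.3.1).

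SAP 3.2 defines exercise, early recovery and late recovery, but not baseline. The 100-140 mg/dL check in Protocol 3.2.1 is an entry condition and is not called baseline.

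**The concern.** A baseline covariate should be measured before treatment can act on it. Here the only samples the plan calls baseline include one drawn five minutes after each active strategy begins, while at the control visit the same sample is untreated. Two natural ways to follow that label are to average the listed samples or to take the last one. Both put a post-intervention value in the model, with a weight of 1/4 or 1. Adjusting for it removes part of whatever the strategy has already done to glucose.

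The exposure is limited to the adjusted estimates and significance tests. The descriptive primary comparison and the power table do not use the covariate. Even if nothing has moved by 0 minutes, two analysts could compute different covariates and apply the analysis-set rule differently.

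**Working it through.** **1. The plan's own figure.** Paired t-test with n = 16, SD 40 mg/dL per treatment and two-sided alpha 0.05 (Protocol 6.1, SAP 2.0). The standard error of the mean difference is 40 × √(2(1 − r)) / √16. At r = 0.5 this is 40 × 1 / 4 = 10 mg/dL. With a true difference of 30 mg/dL and 15 degrees of freedom, the noncentral t gives power of 80.1%; the table says 80%. At r = 0.2 and r = 0.8 the standard error is 12.65 and 6.32 mg/dL.

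**2. The bias.** Let X be pre-intervention glucose, T = 1 for glucagon and 0 for control, and Y = a + bX + τT + error. If glucagon has changed glucose by e at 0 minutes and that sample has weight w in the covariate, the covariate is C = X + w·e·T. Substituting, Y = a + bC + (τ − b·w·e)T + error, so the adjusted difference is shifted by −b × w × e.

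**3. Inputs.** w is 1/4 for the mean of the four samples, 1 for 0 minutes alone, and 0 for pre-intervention samples only. Neither b nor e is in the documents. Protocol 4.2.1 describes glucagon as acting rapidly but gives no figure. Assumed ranges: b = 0.5 to 1, e = 0 to 10 mg/dL.

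**4. Loss in the strategy 3 versus control estimate (mg/dL).**

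| e | b | w = 1/4 | w = 1 |
|---|---|---|---|
| 0 | any | 0 | 0 |
| 5 | 0.5 | 0.625 | 2.5 |
| 5 | 1 | 1.25 | 5 |
| 10 | 0.5 | 1.25 | 5 |
| 10 | 1 | 2.5 | 10 |

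The largest losses are 2.5/10 = 0.25 and 10/10 = 1.0 standard errors at r = 0.5. Over r = 0.2 to 0.8 they are 0.20 to 0.40 (w = 1/4) and 0.79 to 1.58 (w = 1).

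**5. Simulation check.** 12,000 runs per setting; 16 pairs; starting glucose uniform over 100-140 mg/dL; assumed sample noise SD 3 and residual SD 28.3 per visit; true difference 30; within-pair regression with a period term; no drift between −30 and 0 minutes. Monte Carlo error is about 0.1. Mean adjusted difference by covariate:

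| b | e | −30/−15 mean | −30/−15/−5 mean | Four-sample mean | 0 min alone |
|---|---|---|---|---|---|
| 0.5 | 0 | 29.9 | 29.9 | 29.9 | 29.9 |
| 1 | 0 | 30.0 | 30.0 | 30.0 | 30.0 |
| 0.5 | 5 | 30.1 | 30.1 | 29.5 | 27.7 |
| 1 | 5 | 30.2 | 30.2 | 29.0 | 25.6 |
| 0.5 | 10 | 30.1 | 30.1 | 28.9 | 25.4 |
| 1 | 10 | 30.1 | 30.1 | 27.7 | 20.8 |

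In the last row the loss with 0 minutes alone is 30.1 − 20.8 = 9.3, slightly under the formula's 10. The formula's b is the fitted slope, and sample noise attenuates it: starting-glucose variance is 40²/12 = 133.3 and noise variance 3² = 9, so the factor is 133.3/142.3 = 0.94 and the expected loss 9.4. The fitted slope had an SD of about 0.69 across runs, so the bias realised in a single trial of 16 is itself uncertain.

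**6. Other comparisons.** Against strategy 1 the shift depends on the difference between the two five-minute effects. Protocol 1.1 says basal reductions need 60-90 minutes to lower circulating insulin by the start of exercise, so strategy 1's shift at 0 minutes is probably near nil and the bias close to that against control. Strategy 2 may also have moved glucose by then, so no size or direction is given for strategy 3 versus 2. None is given for the logistic models either.

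**The case against.** The strongest reply is that this is a gap in specification, not a demonstrated error. The sampling schedule groups blood draws under headings and does not define a covariate; it states neither an averaging rule nor a last-value rule, so a pre-intervention value remains open to the analyst. That stands, and the point is worded accordingly.

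The sizes rest on assumed inputs. Nothing in the documents supports a 10 mg/dL rise within five minutes. The lower limit of 0.5 for b is also unsupported, since an outcome covering 75 minutes, with nadir values carried forward, may depend less on starting glucose. This also stands: the 10 mg/dL loss needs 0 minutes alone, b = 1 and e = 10 together and should not be read as an expected value.

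The trial is described as a feasibility study with a descriptive primary analysis, and if glucagon has raised glucose by 0 minutes, the bias against control works against the product. Both are true and keep the point minor. Neither settles which covariate the specified tests use.

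Lastly, earlier samples may predict less well if glucose is drifting, and Protocol 3.2.1 allows oral or IV glucose on arrival without saying how long before the −30 sample. That is a real cost, sized with the remedy; it is too small to justify keeping a post-intervention covariate.

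**Conclusion.** The concern holds and is minor. The textual facts are certain: 0 minutes is listed as baseline, all three active strategies have begun by then, and baseline glucose is not defined where the models and the analysis set use it. The bias is conditional. It is nil if glucose has not moved by 0 minutes or if the analyst uses pre-intervention samples. Under the assumed ranges it is at most 2.5 mg/dL with the four-sample mean, which is small, and up to 10 mg/dL in the extreme case with 0 minutes alone. At an intermediate e of 5 mg/dL the losses are 0.6 to 1.25 and 2.5 to 5 mg/dL. These figures show scale; they are not evidence for the values of b or e.

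**What to change.** Add one sentence to SAP 3.3.1, applying also to SAP 3.4.1 and to the analysis-set rule: baseline glucose is computed only from samples drawn before the intervention, by one rule used at every visit, control included. An example is the mean of −30, −15 and −5 minutes if the −5 draw precedes the intervention by procedure, and otherwise the mean of −30 and −15. The documents do not state that order, so the sponsor must confirm it. State also that the 0-minute sample is neither a covariate nor counted towards the baseline requirement. It stays outside the exercise outcome, whose samples begin at 5 minutes.

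No new samples or protocol change are needed; the SAP sentence can note that it governs the covariate despite the heading in Protocol 3.2.4. The SAP's version history records that no analyses had been performed, so on that record the rule can still be pre-specified.

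The cost is a possible small loss of precision. With no drift (b = 1, e = 0), the SD of the adjusted estimate was 10.40 with the −30/−15 mean and 10.38 with the four-sample mean. Drift makes the cost larger. Suppose a linear drift of SD 15 mg/dL from −30 to 0 minutes and b = 1. The −30/−15 mean is centred at −22.5 minutes and misses 0.75 of the drift, giving a residual SD of √(28.3² + 11.25²) = 30.5. The four-sample mean is centred at −12.5 and misses 0.417 of it, giving √(28.3² + 6.25²) = 29.0. The ratio is 1.05, so the loss is about 5% of the SD even under that sizeable drift.

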535 higher compared with the Xeris 0.5 mg and 1 mg groups. The incidences of all remaining AEs
536 were low and not notably different across treatment groups.

537
538 However, as reported by Haymond (15), when subcutaneous glucagon in dosages of 20–150 µg was
539 given to children to manage impending hypoglycemia due to gastroenteritis or poor oral intake of
540 carbohydrates, it did not result in a perceived worsening of the patient’s nausea, nor did it result in
541 emesis immediately after glucagon administration, as is commonly observed with the recommended
542 single large 500–1,000 µg rescue dose.

543
544 In Xeris’ completed Phase 2a safety/PK/PD study, Protocol No. XSMP-201, which tested 75–300
545 µg G-Pen Mini™ doses in adult T1D patients, neither nausea nor vomiting were observed with
546 doses of 75-150 µg. Nausea, but not vomiting was reported by 4/12 subjects given the 300 µg dose
547 (3 mild, 1 moderate). Since doses of subcutaneous G-Pen Mini™ (glucagon injection) given to
548 adults per this protocol will range from 75–300 µg, some nausea is possible, but the incidence is
549 expected to be relatively low and severe nausea is not expected.

550 Although available data from prior studies indicate that mini-dose glucagon is likely to successfully
551 treat mild to moderate hypoglycemia, this is not definitively proven. Therefore, there is a risk that
552 mini-dose glucagon will not work as well as glucose tablets or other oral carbohydrates and if this is
553 the case, severe hypoglycemia could result.

554 Endurance exercise, as will be performed in this study, may be associated with generalized fatigue
555 and mild to moderate hypoglycemia. In rare situations, exercise can promote myocardial infarction,
556 sudden cardiac death or arrhythmias. In persons who have proliferative retinopathy, exercise that
557 increases blood pressure significantly (>180 mmHg) can promote retinal bleeding (PMID:
558 21800941). Since all participants will be screened prior to the exercise test for diabetes-related
559 complications and glucose monitoring will be performed throughout the experiments, the risk of a
560 serious exercise-associated adverse event will be extremely remote.

561

562 The blood draws and IV placement could result in discomfort or bruising, or rarely, an infection or a
563 blood clot. Fainting may also occur. The exact blood volumes collected may vary according to

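### The adverse event comparison borrows a logistic mixed model that breaks down when a strategy has no events; exact intervals and paired counts should replace it

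*SAP*

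**What the plan says.** SAP 4.1.2 lists proportions and counts of adverse events by strategy. It then says "Adverse events will be tabulated by MedDRA categories with frequencies compared between" and continues "strategies. Similar diagnostics and models will be performed as described for the efficacy" outcomes. Protocol 6.3 matches: "strategies. Similar models and diagnostics will be performed as described for the efficacy outcomes".

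The binary method being borrowed is in SAP 3.4.1. It is a logistic mixed model used to "assess differences between strategy 3 and each of the other strategies. The model will be" adjusted for baseline glucose and any period effect. Tests are two-sided at 0.05, with no multiplicity correction. That section also promises a percentage with a 95% confidence interval by strategy, without naming the interval method.

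The SAP does not say whether the model's p-values are Wald or likelihood-ratio. It sets no minimum event count and gives no rule for a strategy with zero events. On expected rates, Protocol 4.2.1 says only that nausea incidence is "expected to be relatively low and severe nausea is not expected". It reports no nausea or vomiting at 75-150 µg in an earlier study, and nausea in 4 of 12 subjects at 300 µg.

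**The concern.** The trial was sized on glucose, not on adverse events. SAP 2.0 gives 16 completers as the target, "selected as a reasonable sample size for this feasibility study. Considering the primary outcome", and its power table covers glucose only. That gives about 16 sessions per strategy.

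Adverse events will be sparser than the binary efficacy outcomes. Under SAP 4.1.1, hypoglycemic, hyperglycemic, injection-related and exercise-induced events count as adverse events only when extra criteria are met. Empty cells are therefore to be expected.

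A logistic model with an empty strategy has no finite estimate for that contrast, so its p-value reflects the software's test and stopping rule more than the counts. At stake is the safety table for a preparation that Protocol 1.3 describes as not FDA approved. It could show p-values near 1 beside a visible imbalance, or a nominally significant result on three events.

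**Working it through.** **Inputs.** 16 completers in a 4-way crossover, so 16 sessions per strategy and 64 in all (SAP 2.0). Two-sided 0.05 and the logistic model (SAP 3.4.1). Nausea 4/12 = 33% at 300 µg (Protocol 4.2.1). The comparator adverse event rate is not in the documents; it is assumed to be 0%, with a range to 10%.

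**The plan's own figure.** The documents give no power or precision for adverse events, only for glucose: "Power was calculated for a sample size of 16 participants with a two-sided alpha of 0.05 and assuming a standard" deviation of 40 mg/dL. For a 30 mg/dL difference and correlation 0.5, the SD of the difference is 40 × √(2 × (1 − 0.5)) = 40. The noncentrality is 30/(40/√16) = 3 on 15 df, and power is 80.06% against the stated 80%. All 28 cells reproduce within one point. The table is sound but says nothing about adverse events.

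**How likely is an empty cell?** P(no event in 16) = (1 − p)^16, which is 44% at a true rate of 5% and 19% at 10%.

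**What the model does with one.** In a fixed-effects logistic fit of k of 16 on glucagon against 0 of 16, the coefficient runs off towards infinity. The fit stops at a standard error of about 12,049, so the Wald p-value is about 0.999 for every k tried from 1 to 10. With all four strategies, period and simulated baseline glucose in the model, the median Wald p-value was also about 0.999 at 5, 6, 8 and 10 events. A participant random intercept does not supply the missing comparator events, so the separation remains.

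The likelihood-ratio test behaves differently. Let L(a,n) = a ln(a/n) + (n − a) ln((n − a)/n). At 3 against 0:

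- Unpaired: 2 × [L(3,16) + L(0,16) − L(3,32)] = 2 × (−7.721 + 0 + 9.956) = 4.47, p ≈ 0.035.
- Paired, conditional: 2 × 3 × ln 2 = 4.16, p = 0.041.
- Exact paired (McNemar): 2 × 0.5^3 = 0.25.

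The same three events thus give about 0.999, 0.035 or 0.25.

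**The exact paired test.** With k discordant pairs all one way, p = 2 × 0.5^k: 5 against 0 gives 0.0625, and 6 against 0 gives 0.031. With no comparator events, power is P(X ≥ 6) for X ~ Bin(16, p):

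| True glucagon rate | Power |
|---|---|
| 10% | 0.3% |
| 15% | 2.4% |
| 20% | 8.2% |
| 33% | 45% |

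If the comparator rate is 5% or 10%, with sessions independent, power at 33% falls to 28% or 16%.

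**What can be said at this size.** The exact 95% upper limit for 0/16 is 1 − 0.025^(1/16) = 20.6%. For 1/16 the interval is 0.2% to 30.2%, and for 2/16 it is 1.6% to 38.3%.

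**The case against.** The strongest reply is that the SAP says only that the models will be similar, in a feasibility study whose secondary outcomes are largely descriptive. An analyst could decline to model sparse categories. SAP 3.4.1 already promises 95% intervals for binary outcomes, and SAP 4.1.2 already lists counts and proportions. Baseline glucose is also a sensible covariate for hypoglycemic and hyperglycemic events. All of this is fair, and it narrows the change needed. It does not remove the borrowed model, name an exact interval or provide for an empty cell. The one fallback, for skewed residuals, does not address separation.

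A reader might also infer more than the documents support:

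- **That the comparison cannot detect the rates expected.** No numeric rate is given for this trial. At the one reported rate, 33%, power is 45% by exact McNemar, 66% by Fisher's exact test and 74% by a pooled normal formula. That is low, but it is not nil.
- **That the result is almost certain to be non-significant.** This depends on the test. If likelihood-ratio tests reject from 3 against 0, the chance of 3 or more of 16 is 21%, 65% and 94% at 10%, 20% and 33%. Those rejections come too easily, since the exact p-value at that threshold is 0.25.
- **That non-significance will be reported as safety.** Neither document says so. The risk is that a reader takes it that way.
- **That the sample size is wrong.** Low power for adverse events is normal in a feasibility trial.

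**Conclusion.** The concern holds as a defect of method. Carried over to sparse adverse events, the efficacy model gives a p-value that turns on an unstated choice of test: about 0.999, 0.035 or 0.25 for the same 3 against 0. The valid alternative, an exact paired test, has power of about 8% or less for glucagon rates up to 20% and 45% at 33%. A non-significant comparison is therefore not evidence of no difference.

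This rests on about 16 sessions per strategy, a comparator rate of zero (power is lower at 5% or 10% for the 20% and 33% glucagon rates), and a fixed-effects version standing in for the mixed model. The safety set takes in all subjects, so replaced participants could add a few sessions; that would not change the conclusion. The primary analysis and sample size are unaffected. The change should be made, but it is one of wording.

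**What to change.** In SAP 4.1.2 and Protocol 6.3, replace the sentence that applies the efficacy models with text to this effect:

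- For any adverse event and for each MedDRA category, report participants with the event over participants exposed, by strategy, with exact (Clopper-Pearson) 95% intervals. Give the upper limit when the count is zero (20.6% for 0/16).
- For strategy 3 against each comparator, give the number of participants with the event on strategy 3 only, on the comparator only, and on both.
- If a test is kept, use an exact paired (McNemar) test, and state that a non-significant result is not evidence of no difference.

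The cost is a wording change in two documents, with no new data and less modelling than planned. The small downside is that there will be no model-adjusted p-values for adverse events.
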